## Evaluation of clinical efficacy of different doses of LT4 in the treatment of pregnant women with normal-high TSH and positive TPOAb in the first half of pregnancy

### **Research background and purpose**

Thyroid hormone (TH) is essential for fetal brain development. The fetal thyroid develops at 8-12 weeks and matures at 18-20 weeks to function. Therefore, fetal development in the first half of pregnancy (gestational age  $\leq$  20 weeks) depends largely on the supply of maternal TH. Normal-high TSH value: It is a thyroid function state unique to women in the pre-pregnancy and pregnancy period; thyroid autoantibodies (mainly TPOAb) during pregnancy reflect the thyroid autoimmune state. TPOAb positivity is considered to be a mild thyroid dysfunction, which can affect placental function through inflammatory reactions such as IL-6, IL-8, IL-10 and tumor necrosis factor  $\alpha$ , and increase the risk of adverse pregnancy outcomes such as miscarriage. The intestinal microbiota also plays a vital role in shaping and regulating the immune system and immune response. Our research group studied the biological characteristics of the intestinal flora in patients with hypothyroidism during pregnancy and abnormal TPOAb and found that abnormal TPOAb was associated with intestinal flora.

Normal-high TSH with positive TPOAb is associated with adverse pregnancy outcomes such as miscarriage, premature birth, premature rupture of membranes, preeclampsia, placental abruption, and fetal growth restriction. Taking levothyroxine (LT4) can reverse the harmful effects of TPOAb and TGAB levels, improve patients' thyroid function, and reduce the incidence of adverse pregnancy outcomes such as gestational diabetes, premature rupture of membranes, miscarriage, premature birth, and macrosomia. The "Guidelines for the Prevention and Management of Thyroid Diseases During Pregnancy and Childbirth" pointed out that in early pregnancy, when TSH is between 2.5mIU/L and the upper limit of the pregnancy reference value (or 4.0mIU/L in early pregnancy) with positive TPOAb, 25ug-50ug LT4 should be given for treatment. However, high-dose LT4 may have adverse reactions such as palpitations, insomnia, sweating, and nausea. Therefore, this study explored the differences in clinical efficacy of different doses of LT4 in the treatment of pregnant women with normal-high TSH and positive TPOAb.

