### **Research plan**

#### **1. Research content**

Pregnant women diagnosed with normal-high TSH and positive TPOAb before 20 weeks of pregnancy who received perinatal care and gave birth in the Third Affiliated Hospital of Zhengzhou University from July 2019 to October 2023 were selected and divided into two groups, A and B, with 100 cases in each group according to the dose of LT4 of 25ug and 50ug; those who did not take LT4 were group C, with 200 cases. The clinical efficacy of different doses of LT4 in the treatment of pregnant women with normal-high TSH and positive TPOAb in the first half of pregnancy was explored.

Inclusion criteria: (1) Diagnosed with normal-high TSH and positive TPOAb before 20 weeks of pregnancy (TSH: 2.5mIU/L-upper limit of reference range, TPOAb  $>$  34IU/mL), FT4 in the normal range (FT4: 12-22pmol/L) in line with the diagnostic criteria established by the Laboratory Department of the Third Affiliated Hospital of Zhengzhou University; (2) All subjects voluntarily participated and signed informed consent

Exclusion criteria: (1) Multiple pregnancy (2) Assisted reproductive technology; (3) Suffering from

serious diseases or diseases that affect pregnancy outcomes, such as dysfunction of important organs; (4) Suffering from thyroid disease; (5) Diagnosed with a history of other endocrine, antiphospholipid syndrome and other autoimmune diseases; (6) Taking drugs that affect the thyroid gland (7) LT4 allergy

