## 2. Research steps

- ① Select pregnant women who meet the inclusion and exclusion criteria and group them, and record the basic information of the pregnant women, mainly including: age, height, weight, pregnancy and delivery history, thyroid function and other serological indicators.
- ② Collect blood and stool samples from pregnant women in groups A and B before and after LT4 treatment, track thyroid function indicators such as TSH, FT4, TPOAb before and after treatment in the three groups of pregnant women, and record maternal and fetal nutritional development.
- ③ Pregnancy outcomes: Track and follow up maternal and fetal outcomes, including the incidence and mode of delivery of adverse pregnancy outcomes such as miscarriage, premature birth, gestational hypertension, gestational diabetes, premature rupture of membranes, fetal growth restriction, macrosomia, intrapartum blood loss, neonatal sex, weight, head circumference, height, Apgar score, thyroid disease, etc.
- ④ Statistical methods: SPSS 26.0 software was used for statistical analysis; continuous data were described by (mean  $\pm$  standard deviation), and count data were expressed by frequency and rate; two independent samples that met normal distribution and homogeneity of variance were analyzed by t test and corrected t test; comparison of binary data between two independent samples of count data was analyzed by X test and corrected X test; P < 0.05 was considered statistically significant.

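### Seventeen or more outcomes are judged at an unadjusted P < 0.05 with no primary outcome, designated contrast or multiplicity rule; if each is tested B versus A, the chance of a false dose finding is roughly 35% to 58%, not 5%

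*Combined protocol and SAP*

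**What the plan says.** All references are to the combined protocol and SAP.

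- **Aim.** Research background and purpose: "this study explored the differences in clinical efficacy of different doses of LT4".
- **Groups.** Section 1, Research content: women "were selected and divided into two groups, A and B, with 100 cases in each group according to the dose of LT4", and "those who did not take LT4 were group C, with 200 cases". The sampling frame is women "who received perinatal care and gave birth" at the study hospital.
- **Thyroid outcomes.** Section 2, step 2: "track thyroid function indicators such as TSH, FT4, TPOAb before and after treatment in the three groups of pregnant women".
- **Pregnancy and neonatal outcomes.** Section 2, step 3 gives a list that includes "gestational hypertension, gestational diabetes, premature rupture of membranes, fetal growth restriction, macrosomia, intrapartum blood loss, neonatal sex, weight, head circumference" and ends open.
- **Tests.** Section 2, step 4: "two independent samples that met normal distribution and homogeneity of variance were analyzed by t test and corrected t test". Binary data get an ordinary or corrected chi-square test, also for two samples.
- **Decision rule.** Section 2, step 4: "P < 0.05 was considered statistically significant".

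No section names a primary outcome, says which pair of groups decides the study question, or gives a multiplicity rule. The corrections mentioned for the t and chi-square tests are presumably those for unequal variances and continuity. Nothing presents them as multiplicity adjustments.

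**The concern.** The study asks whether LT4 dose changes clinical efficacy, but the plan does not fix which outcome answers that question, and it leaves the contrast to be inferred. With many outcomes each judged at 0.05, one or more will often cross the threshold by chance. Whichever does could be presented as the dose effect, with an apparent 5% error rate that does not describe how the result was found. A reader of the results could not tell whether a significant outcome was the one the study set out to test or the one that happened to come up.

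**Working it through.** The plan gives no error-rate or power figure to reproduce, so the check starts from the outcome list.

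**Step 1: count the outcomes.**

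| Source (section 2) | Outcomes | Number |
|---|---|---|
| Step 2 | TSH, FT4, TPOAb | 3 |
| Step 3 | Mode of delivery | 1 |
| Step 3 | Adverse pregnancy outcomes, from miscarriage to macrosomia | 7 |
| Step 3 | Blood loss, and the neonate's weight, head circumference, length, Apgar score and thyroid disease | 6 |

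The total is 3 + 1 + 7 + 6 = 17. Neonatal sex is left out because it is not plausibly a treatment outcome; counting it gives 18. If miscarriage cannot occur among women selected for having given birth, the count is 16. Both lists are open-ended.

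**Step 2: tests at exact 5% size.** Assumptions: each outcome is tested B versus A, two-sided (the plan does not state sidedness); dose has no effect; A and B are comparable.

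Independent outcomes: P(at least one) = 1 − 0.95^17 = 0.582. The expected number of false positives is 17 × 0.05 = 0.85.

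For test statistics with a common correlation ρ:

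P = 1 − ∫ φ(u) [Φ((1.96 − √ρ·u)/√(1−ρ)) − Φ((−1.96 − √ρ·u)/√(1−ρ))]^k du

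| Outcomes k | ρ = 0 | ρ = 0.3 | ρ = 0.5 |
|---|---|---|---|
| 16 | 56.0% | 47.6% | 37.4% |
| 17 | 58.2% | 49.3% | 38.6% |
| 18 | 60.3% | 50.9% | 39.8% |

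The documents give no correlation; 0 to 0.5 is an assumed range.

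**Step 3: allow for discrete tests.** Chi-square tests on uncommon events can reject less than 5% of the time, more so with a continuity correction. The plan gives no event rates and does not say when the correction applies, so both were varied. The simulation used 100 women per group, 8 continuous and 9 binary outcomes (the seven adverse outcomes, mode of delivery as two categories, and neonatal thyroid disease), 6,000 runs per setting, and correlation on the underlying patient scale. The Monte Carlo standard error is about √(0.5 × 0.5/6000) = 0.6 percentage points.

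| Assumed event rates | Chi-square rule | Correlation 0 | Correlation 0.5 |
|---|---|---|---|
| Middle (2% to 45%) | Uncorrected | 57.1% | 47.0% |
| Middle | Corrected if expected count < 5 | 54.0% | 44.5% |
| Middle | Corrected throughout | 45.4% | 36.6% |
| Low (1% to 40%) | Uncorrected | 54.6% | 46.1% |
| Low | Corrected if expected count < 5 | 48.7% | 37.8% |
| Low | Corrected throughout | 43.0% | 33.0% |
| High (5% to 50%) | Uncorrected | 58.8% | 47.1% |
| High | Corrected if expected count < 5 | 58.0% | 47.2% |
| High | Corrected throughout | 49.9% | 37.6% |

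The extremes are 33% and 59%; roughly 35% to 58% is a fair summary. That is about 7 to 12 times the nominal 5% (35/5 = 7; 58/5 = 11.6).

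**Step 4: the other contrasts.** Three groups allow three pairwise comparisons, so 3 × 17 = 51 tests. The figures above count only B versus A. No combined figure is given here, because contrasts that share a group are not independent.

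**The case against.** The strongest reply is that the study is exploratory. The stated purpose is to explore differences, and the plan claims no power and no confirmatory conclusion. That softens the point but does not remove it: the title speaks of evaluating clinical efficacy, and step 4 declares significance at 0.05 without labelling anything exploratory.

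Second, steps 2 and 3 speak of tracking, recording and following up. They do not say that every item gets a B-versus-A test, and the t test is limited to data meeting its distributional conditions. This stands as a condition on the calculation: the figures apply if each listed outcome is tested.

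Third, a reader might infer that the plan has no comparison of interest at all. The documents do not support that. Groups A and B are defined by dose and the question is about dose, so B versus A is implied. It is simply not designated as the deciding contrast among the three available.

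Fourth, a reader might settle on one narrow error rate, such as 43% to 53%. That band needs a particular set of event rates and a particular rule for correcting chi-square, and the plan supplies neither.

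Fifth, the Result section might be read as showing chance findings from this plan. Its groups (disease and control, HA and HB) are not tied to A, B and C, so it does not show how the listed outcomes were tested.

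Finally, grouping is not described as randomised, which may matter more than multiplicity. That is a separate issue: it is excluded from these figures by assumption, and it does not excuse this gap.

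**Conclusion.** The gap is real and should be closed. One unadjusted threshold covers at least 17 listed outcomes in a three-group study, with no primary outcome, no formally designated contrast and no multiplicity rule. The chance of at least one false B-versus-A result is 58% at correlation 0 and 39% at correlation 0.5 for exact 5% tests, and roughly 35% to 58% once event rates and the chi-square correction are allowed to vary. These figures assume that every listed outcome is tested two-sided, that dose has no effect, and that A and B are otherwise comparable. The correlations and event rates are assumptions, not figures from the documents. The absence of a primary outcome and of a multiplicity rule is certain from the text; the exact size is not.

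**What to change.** In section 2, step 4:

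1. Designate B versus A as the single primary contrast on one primary outcome, tested at 0.05. The choice of outcome is the sponsor's: a pregnancy outcome, a composite counted once per woman, or a thyroid index would each fit the stated background.
2. If miscarriage is part of the primary outcome, state how it is counted, given that section 1 selects women who delivered.
3. Report every other listed outcome and contrast with a 95% confidence interval, labelled exploratory, with no claim of significance.
4. If data have already been examined, as the Result section may indicate, say that the primary outcome was chosen post hoc and label all results exploratory.

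**Cost.** Wording and reporting only; no new data. Some nominally significant results become exploratory. A binary primary outcome has low power at 100 per group. For an assumed 40% versus 30%, the standard error is √(2 × 0.35 × 0.65/100) = 0.0675 under the null and √((0.24 + 0.21)/100) = 0.0671 under the alternative, so power is Φ((0.10 − 1.96 × 0.0675)/0.0671) = Φ(−0.48), about 32%. Adjusting every test instead would cost more: Bonferroni over 17 outcomes uses 0.05/17 = 0.0029 and lowers power for an assumed 0.4 SD difference from about 81% to 44%.

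**Limits.** Naming a primary outcome after the data have been seen does not restore a pre-specified 5% test, and none of this addresses confounding from non-random grouping.

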## Safety Analysis

Levothyroxine is a common drug for the treatment of thyroid diseases and has been proven to be safe and effective. The "Guidelines for the Prevention and Treatment of Thyroid Diseases during Pregnancy and Childbirth" recommends that 25ug-50ug levothyroxine (LT4) be given for treatment when TSH in early pregnancy is between 2.5mIU/L and the upper limit of the pregnancy reference value (or 4.0mIU/L in early pregnancy) with positive TPOAb. This study collected feces and a small amount of peripheral blood from patients, which will not have adverse effects on the subjects.

## Feasibility Analysis

Levothyroxine is an effective drug for the treatment of thyroid diseases. It is easily absorbed by the body, has a high utilization rate, and is widely used in clinical practice. The information on the condition of the subjects collected in this study is obtained from routine perinatal care and will not harm their health and rights; the peripheral blood collection in this study is often carried out at the same time as other similar blood test items, without the need for additional blood collection, and the amount of blood collected is small, which causes little harm to the research subjects, and the rest of the samples are collected non-invasively.

## Result

(1) There was no significant difference between the disease group and the control group in general conditions such as age, BMI, gestational age, etc.; (2) The disease group had higher TC and LDL levels than the control group, as well as high-sensitivity C-reactive protein (hsCRP) levels, Th17, Th17/Treg ratio was significantly higher than that of the control group, and the percentages of Treg and IL-10 were significantly lower than the control group; (3) TSH, hsCRP, Th17, Th17/Treg ratio, and TNF- $\alpha$  in the disease group after LT4 intervention were significantly higher decreased, and FT4, Treg, and IL-10 increased significantly; (4) The incidence of SIBO in the disease group was higher than that in the control group, and the incidence of SIBO in the disease group after intervention was lower than before intervention; (5) Compared with the HA group, The TSH level of the HB group was lower and the IL-10 level was higher, but there was no significant difference in the levels of blood lipids such as TC, TG, HDL, LDL and other inflammatory factors such as hsCRP and IL-2 between the two groups; (6) Correlation analysis in pregnant women with normal-high TSH values and positive TPOAb: TSH is positively correlated with hsCRP, negatively correlated with Treg proportion, TPOAb is positively correlated with TNF- $\alpha$ ; IL-10 levels are negatively correlated with IL-2 and IL-4 levels; TC is positively correlated with hsCRP.

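### Result item (3) presents an uncontrolled before/after fall in TSH, the variable used to select women, as a change after LT4, so the fall alone does not show an LT4 effect

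*Combined protocol and SAP*

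**What the plan says.** All references are to the combined protocol and SAP.

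- **Entry.** Section 1 (Research content), inclusion criterion 1, selects on TSH within a window: "TSH: 2.5mIU/L-upper limit of reference range". The study's own upper limit is not given as a number. The background section cites a guideline that uses the "upper limit of the pregnancy reference value (or 4.0mIU/L in early pregnancy"). No repeat or confirmatory TSH is described.
- **Groups.** Groups A and B are formed "with 100 cases in each group according to the dose of LT4 of 25ug and 50ug". The comparator, group C, is planned as 200 untreated women. On a plain reading, all three groups come from the same diagnosed population. No randomisation is described.
- **Follow-up.** Section 2 (Research steps), item 2, plans to "track thyroid function indicators such as TSH, FT4, TPOAb before and after treatment in the three groups of pregnant women". TSH is therefore planned at both times in untreated women too.
- **Analysis.** The statistical methods item in section 2 describes continuous data by mean and standard deviation and names independent-samples t tests. It names no paired test, no baseline adjustment and no comparison of change with group C.
- **Result.** Item (3) reports: "3) TSH, hsCRP, Th17, Th17/Treg ratio, and TNF- $\alpha$ in the disease group after LT4 intervention were significantly higher decreased". It gives no number of women, mean, SD, P value or group C change. The labels used there (disease group, control group, HA, HB) are not mapped to A, B and C.

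**The concern.** When people are selected because a measurement is high, a second measurement tends to lie closer to the average of the population they came from, with no treatment at all. A test of after minus before against zero estimates the LT4 effect plus this regression to the mean plus any trend in TSH over pregnancy. The document does not give the direction of that trend. A correctly paired test has the same problem, because the fault lies in the missing comparison and not in the choice of test.

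The TSH fall in item (3) reads as the direct biochemical evidence that LT4 worked. If part or all of it would also appear in untreated women selected by the same rule, the statement credits LT4 with something the comparison cannot attribute to it. Group C was selected by that rule and should carry the same artefact, so the data that could separate the two are planned but not used for this claim.

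**Working it through.** The plan states no TSH mean, SD, effect size or sample-size calculation, so there is no figure of its own to reproduce. The check asks how large a fall can arise with **no LT4 effect and no time trend**.

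**Inputs from the document:** lower limit 2.5 mIU/L; planned sizes 100 (A), 100 (B) and 200 (C); P < 0.05, taken as two-sided.

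**Assumed, not in the document:** upper limit 4.0 mIU/L (borrowed from the guideline text in the background section); log-normal TSH; source-population median 1.5 to 2.5 mIU/L; log SD σ of 0.5 or 0.6; test-retest correlation ρ of 0.5 to 0.9; 100 women analysed; qualifying test used as the before value.

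**Model.** Let m be the log of the source median. For a woman whose qualifying log TSH is x, the follow-up log TSH has mean m + ρ(x − m) and SD σ√(1 − ρ²). Let d be the mean fall on the untransformed scale and s the SD of the change. The approximate chance of a significant paired result in the direction of d is Φ(d/(s/√n) − 1.96).

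**Three worked cases** (σ = 0.5, ρ = 0.7, n = 100, untransformed scale):

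| Source median | Mean before → after | d | s | d/(s/10) | Chance of P < 0.05 |
|---|---|---|---|---|---|
| 1.6 | 3.04 → 2.67 | 0.37 (12.3%) | 1.00 | 3.7 | Φ(1.74) = 0.96 |
| 2.0 | 3.09 → 2.88 | 0.20 (6.6%) | 1.08 | 1.85 | Φ(−0.11) = 0.46 (0.47 before rounding) |
| 2.5 | 3.14 → 3.12 | 0.02 (0.6%) | 1.16 | 0.17 | Φ(−1.79) = 0.04 |

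**Full grid.** Sixteen scenarios were simulated: median 1.5 or 2.0, σ 0.5 or 0.6, ρ 0.5, 0.7, 0.8 or 0.9, with n = 100.
- Untransformed TSH, the scale implied by mean ± SD and t tests: the mean falls by about 1% to 23%. A paired test finds a significant fall in about 7% to 100% of studies, above 50% in 8 of the 16 scenarios. The low end is at median 2.0, σ = 0.6, ρ = 0.9; the high end is at median 1.5, σ = 0.5, ρ = 0.5.
- The unequal-variance independent-samples t test, closest to the tests the plan names: 3% to 100%, above 50% in 7 of 16.
- Log TSH: geometric mean falls 4% to 30%; paired test significant in 38% to 100%. The plan mentions no log transformation, so these figures are secondary.
- Source median 2.5, untransformed: a significant fall in only 1% to 10%, with no fall or a rise in most scenarios. On the log scale some artefact remains there (at σ = 0.5, chance 0.70 at ρ = 0.5 and 0.17 at ρ = 0.9).

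**Does a contrast with group C remove it?** Under the same no-effect model, comparing change in 100 treated women with change in 200 from group C gave a false-positive rate of 0.051. Regression adjusted for baseline log TSH gave 4% to 6.5%. Both assume that the groups are selected and timed alike. With the planned sizes the difference detectable with 80% power, in SDs of change, is (1.96 + 0.84) × √(1/100 + 1/200) = 0.34 for A or B v C, and 2.80 × √(2/100) = 0.40 for A v B.

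**The case against.** **The baseline may not be the qualifying value.** Section 2 first selects women and records thyroid function, then separately describes samples before and after LT4. If the before value is a later sample, equally correlated with the others, simulation shows no spurious fall and about 5% false positives. This stands: the premise is inferred, so the conclusion is conditional on it.

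**The source population may not sit low enough.** Regression runs toward the mean of TPOAb-positive women, whose TSH distribution is not given, and the upper limit of the entry window weakens the artefact. This also stands. A median of 2.5 or more fits poorly with calling values from 2.5 normal-high, but it cannot be excluded.

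**Other results point to a drug effect.** Item (5) reports lower TSH in HB than in HA, which regression to the mean does not produce if both were selected alike. Item (3) also reports a rise in FT4, which had only to lie within its normal range at entry. Both are fair points, although the dose groups are not described as randomised and could differ at baseline.

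**A stronger reading that does not hold.** A reader might infer that regression to the mean alone accounts for the significant TSH fall, or that LT4 did nothing. The document supports neither: the artefact ranges from near-certain significance to none, depending on quantities that it does not give. Nor does the argument carry over directly to hsCRP, Th17, Th17/Treg or TNF-α in the same sentence. They are not entry criteria and would be affected only through correlation with TSH or TPOAb.

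**Conclusion.** The concern holds in a limited form. Item (3) is an uncontrolled before/after change in the selection variable, and neither it nor the analysis plan uses group C to separate an LT4 effect from regression to the mean and gestational trend. If the qualifying test is the baseline, these can explain some or all of the fall, so the fall by itself is not evidence of an LT4 effect.

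The size cannot be fixed from the document. The ranges above (about 1% to 23% for the fall, about 7% to 100% for significance) show what is possible under the assumed source median, SD, correlation, window and n = 100. They are not estimates for this study. The analysed number behind item (3) is itself unknown. The point calls for a change in analysis and wording; it does not show that the reported fall is spurious.

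**What to change.** - State which TSH measurement is the before value, how many women item (3) covers, and how its group labels map to A, B and C.
- Regress follow-up log TSH on group, with baseline log TSH and gestational weeks at both tests as covariates. Report A v C, B v C and B v A as adjusted ratios with 95% confidence intervals.
- Define the follow-up time in group C. There is no treatment there for a value to come after, so take the follow-up TSH at a gestational age comparable with A and B.
- Show within-group TSH changes as description only, with group C's change beside them.
- Reword item (3) so that the TSH fall is not presented as an LT4 effect unless the contrast with group C supports it. The observed change need not be deleted.

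The cost is one regression on TSH already planned in all three groups, the test dates needed to align follow-up, and some rewording. The reported effect may become smaller. Because grouping is by LT4 use with no randomisation described, it remains an adjusted observational contrast, and the nominal error rate holds only as far as the groups are comparable.
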